APPENDIX 3 ENVIRONMENTAL SAMPLING PROTOCOL

General Environmental Sampling Instructions

LOCATION RECORDING

Record your location at the time of sampling using GPS. Record each sampling site using a Google Maps on iPhone or Android. For more information:

<https://www.wikihow.com/Get-Latitude-and-Longitude-from-Google-Maps>

Record GPS similar to the following and out to more than 5 significant digits:

NJ GPS LOCATION: 39°44'23.2"N 104°56'33.6"W

SINK FAUCET SAMPLING

This protocol can be applied to sample water biofilms from kitchen, bathroom, or outdoor sink faucets.

BEFORE SAMPLING:

1. Faucet should be as dry as possible
2. Avoid sampling a faucet if it has been recently used or is wet
3. If faucet is wet, DO NOT dry off. If possible, return to faucet at another time

SAMPLING

1. Identify the sink faucet and take a picture of it using your cell phone or camera.
2. Obtain one of the sterile dual-tipped Flock swabs.
3. Identify the **point of the sink faucet where water exits**. This is where the sample should be taken.

Note: Depending on the faucet, there might be a metal mesh on the faucet head similar the image to the right (“Step 4 under view”). If so, sample the mesh.

Note: Depending on the faucet, there might be an open pipe which water will directly flow out of. If so, sample up into the pipe.

4. Carefully open a new swab package. To do so, carefully pry open the swab package. Remove the swab by grabbing the **RED** handle and avoid laying the swab down on non-sterile surfaces; keep the swab sterile! **Be careful not to touch anywhere along the swab and only handle the swab by the red handle.**
5. *If mesh sampling* - Firmly and thoroughly swab the **point on the sink faucet where water exits** in a back and forth motion 10 times as well as a circular motion - imagine that you are using the swab to “clean” the surface as completely as possible. Twist the swab over and sample the same surface 10 more times to ensure this side of the swab has also collected biofilms. Avoid moving your hand onto the white applicator stick.

OR

If open pipe sampling – Insert the swab into the pipe and swab the sides of the pipe using a circular, firm stirring motion - similar to stirring your coffee – 10 times. Twist the swab over and sample the same surface 10 more times to ensure all sides of the swab has collected pipe biofilm. Avoid moving your hand onto the white applicator stick.

6. Once you have collected the sample, twist and remove the cap from the sterile collection tube that remains in the swab package and **CAREFULLY** place the soiled swab into the transport tube, being careful not to touch the swab tips with your fingers.
7. Cap tightly. Label the tube with a Sharpie or pre-prepared label that contains at a minimum the following information: the date, your initials, sample ID, and sample type (*i.e.*, bathroom sink mesh or hospital room sink faucet pipe).
8. Place labeled tubes in a ziploc bag and refrigerate samples until processing.

DUST SAMPLING

1. Locate a dusty area at the sampling site – sample similar sites in all rooms of NJH and SJH.
2. Before sampling, take a representative picture of the dusty area using your cell phone or camera.
3. Obtain one of the sterile dual-tipped Flock swabs.
4. Carefully open a new swab package. To do so, carefully pry open the swab package. Remove the swab by grabbing the **RED** handle and avoid laying the swab down on non-sterile surfaces; keep the swab sterile! **Be careful not to touch anywhere along the swab and only handle the swab by the red handle tip.**
5. Swab across the dusty surface using a back and forth motion 10 times, imagining that you are using the swab to clean the surface and remove as much dust as possible (refer to the image below). It often helps to rotate the tip of the swab as you brush it across the surface to make sure all sides of the swab get coated with visible dust.
6. Once you have collected the sample, twist and remove the cap from the sterile collection tube that remains in the swab package and CAREFULLY place the soiled dust swab into the transport tube, being careful not to touch the swab tips with your fingers.
7. Cap tightly. Label the tube with a Sharpie or pre-prepared label that contains at a minimum the following information: the date, your initials, sample ID, and sample type (*i.e.*, dust).
8. Place labeled tubes in a ziploc bag and refrigerate samples until processing.

SAMPLING SHOWER HOSES AND SHOWERHEADS

HOW TO SAMPLE THE HOSE (if it has a removable showerhead):

1. Take a representative picture of the end of the showerhead system similar to what is shown in the image using your cell phone or camera
2. *Carefully* twist and remove the showerhead from the shower hose at the connection point labeled “1” on the image to the left. **Do not place the showerhead or hose down**; keep holding both in one of your hands.
3. Obtain **two** of the sterile dual-tipped Flock swabs.
4. Carefully open a new swab package. To do so, carefully pry open the swab package. Remove the swab by grabbing the **RED** handle and avoid laying the swab down on non-sterile surfaces; keep swab sterile! **Be careful not to touch anywhere along the swab and only handle the swab by the red handle tip.**
5. Firmly and thoroughly, swab the inner portion of the hose at point “2” as shown on the image above. Using a “stirring” motion move the swab in and around the hose opening - imagining that you are using the swab to clean the surface or motion similar to stirring your coffee. Rotate the swab as you swirl to ensure all portions of the swabs have been exposed to biofilms. Rotate and swab 10 times. Avoid moving your hand onto the white applicator stick.
6. Once you have collected the sample from the hose, the hose can now be placed down into the tub or onto a counter. **However, keep holding the showerhead.** Twist and remove the cap from the sterile collection tube that remains in the swab package and **CAREFULLY** place the soiled swab into the transport tube, being careful not to touch the swab tips with your fingers.
7. Cap tightly. Label the tube with a Sharpie or pre-prepared label that contains at a minimum the following information: the date, your initials, sample ID, and sample type (*i.e.*, showerhead (SHB) hose).
8. Place labeled tubes in a ziploc bag and refrigerate swab until processing.

HOW TO SAMPLE THE SHOWERHEAD FACE:

1. Carefully open a new swab package. To do so, carefully pry open the swab package. Remove the swab by grabbing the **RED** handle and avoid laying the swab down on non-sterile surfaces; keep swab sterile! **Be careful not to touch anywhere along the swab and only handle the swab by the red handle tip.**
2. Firmly and thoroughly, swab the face of the showerhead (the side from which the water would emerge) at point “3” as shown on the image above. Move the swab back and forth and around the entire surface of the showerhead face 10 times in a circular motion - imagining that you are using the swab to clean the surface as completely as possible. Don't forget to get into the grooves on the showerhead face. Twist the swab over and sample the

same surface 10 more times to ensure this side of the swab has also collected biofilms. Avoid moving your hand onto the white applicator stick.

3. It is now OK to put the showerhead down into the tub or onto a counter.
4. Once you have collected the sample, twist and remove the cap from the sterile collection tube that remains in the swab package and CAREFULLY place the soiled swab into the transport tube, being careful not to touch the swab tips with your fingers.
5. Cap tightly. Label the tube with a Sharpie or pre-prepared label that contains at a minimum the following information - the date, your initials, sample ID, and sample type (*i.e.*, showerhead biofilm (SHB)).
6. Place labeled tubes in a ziploc bag and refrigerate swab until processing.

HOW TO SAMPLE A NON-REMOVABLE SHOWERHEAD:

Locate the showerhead in your home that is most often used. Swabbing should be done when then showerhead is as dry as possible — do not use a showerhead that has been recently used or is wet.

1. Locate the non-removeable showerhead. Take a representative picture using your cell phone or camera.
2. Carefully open a new swab package. To do so, carefully pry open the swab package. Remove the swab by grabbing the **RED** handle and avoid laying the swab down on non-sterile surfaces; keep swab sterile! **Be careful not to touch anywhere along the swab and only handle the swab by the red handle tip.**
3. Firmly and thoroughly, swab the **OUTSIDE SURFACE** of the showerhead (the side from which the water would emerge) using a firm back and forth as well as a circular motion, imagining that you are using the swab to clean the showerhead surface as completely as possible. Don't forget to get into the grooves on the showerhead face. Twist the swab over and sample the same surface 10 more times to ensure this side of the swab has also collected biofilms. Avoid moving your hand onto the white applicator stick.
4. Once you have collected the sample, twist and remove the cap from the sterile collection tube that remains in the swab package and CAREFULLY place the soiled swab into the transport tube, being careful not to touch the swab tips with your fingers.
5. Cap tightly. Label the tube with a Sharpie or pre-prepared label that contains at a minimum the following information - the date, your initials, sample ID, and sample type (*outside SHB*).
6. Place labeled tubes in a ziploc bag and refrigerate swab until processing.

ICE MACHINE SAMPLING

1. Locate the ice machine. Take a representative picture of the ice machine using your cell phone or camera. Be sure to capture both the ice and water spouts.
2. Obtain one of the sterile dual-tipped Flock swabs.
3. Carefully open a new swab package. To do so, carefully pry open the swab package. Remove the swab by grabbing the **RED** handle and avoid laying the swab down on non-sterile surfaces; keep swab sterile! **Be careful not to touch anywhere along the swab and only handle the swab by the red handle tip.**
4. Insert the swab up into the plastic ice dispensing “shoot” – highlighted in red in the image below.
5. Firmly and thoroughly, swab all sides of the plastic ice shoot using a “stirring” motion to move the swab in and around the opening - imagine that you are using the swab to methodically clean the surface. Rotate the swab as you swirl to ensure all portions of the swab has been exposed to biofilms. Rotate and swab 10 times. Avoid moving your hand onto the white applicator stick.
6. Once you have collected the sample, twist and remove the cap from the sterile collection tube that remains in the swab package and **CAREFULLY** place the soiled dust swab into the transport tube, being careful not to touch the swab tips with your fingers.
7. Cap tightly. Label the tube with a Sharpie or pre-prepared label that contains at a minimum the following information: the date, your initials, sample ID, and sample type (*i.e.*, ice machine).
8. Repeat steps 2-7 for the water spout on the ice machine.
9. Place labeled tubes in a ziploc bag and refrigerate swabs until processing.

DRINKING FOUNTAIN SAMPLING

Sampling should be done when the spigot is as dry as possible—avoid sampling a spigot if it has been recently used or is wet. If spigot is wet, DO NOT dry off. If possible, return to faucet at another time.

1. Locate the drinking fountain. Take a representative picture of the drinking fountain using your cell phone or camera.
2. Obtain one of the sterile dual-tipped Flock swab.
3. Carefully open a new swab package. To do so, carefully pry open the swab package. Remove the swab by grabbing the **RED** handle and avoid laying the swab down on non-sterile surfaces; keep swab sterile! **Be careful not to touch anywhere along the swab and only handle the swab by the red handle tip.**

4. *If mesh sampling* - Firmly and thoroughly swab the **point on the spigot where water exits** in a back and forth motion 10 times as well as a circular motion - imagine that you are using the swab to “clean” the surface as completely as possible. Twist the swab over and sample the same surface 10 more times to ensure this side of the swab has also collected biofilms. Avoid moving your hand onto the white applicator stick.

OR

- If open pipe sampling* – Insert the swab into the pipe and swab the sides of the pipe using a circular, firm stirring motion - similar to stirring your coffee – 10 times. Twist the swab over and sample the same surface 10 more times to ensure all sides of the swab has collected pipe biofilm. Avoid moving your hand onto the white applicator stick.
5. Once you have collected the sample, twist and remove the cap from the sterile collection tube that remains in the swab package and **CAREFULLY** place the soiled swab into the transport tube, being careful not to touch the swab tips with your fingers.
 6. Cap tightly. Label the tube with a Sharpie or pre-prepared label that contains at a minimum the following information: the date, your initials, sample ID, and sample type (*i.e.*, left drinking fountain).
 7. Place labeled tubes in a ziploc bag and refrigerate samples until processing.

WATER FEATURE SAMPLING

1. Locate the water feature. It may be a fountain, pool, or water wall. Take a representative picture of the water feature before sampling using your cell phone or camera.
2. Obtain one of the sterile dual-tipped Flock swabs.
3. Carefully open a new swab package. To do so, carefully pry open the swab package. Remove the swab by grabbing the **RED** handle and avoid laying the swab down on non-sterile surfaces; keep swab sterile! **Be careful not to touch anywhere along the swab and only handle the swab by the red handle tip.**
4. Sample the dry “scumline” (see image of a pool below) – located at the air-water interface. Rotate the swab around as you sample the dry area right above the water line (see image of a pool below) and ensure all portions of the swab has been exposed to the biofilm. Rotate and swab 10 times. Avoid moving your hand onto the white applicator stick.
5. Once you have collected the sample, twist and remove the cap from the sterile collection tube that remains in the swab package and **CAREFULLY** place the soiled swab into the transport tube, being careful not to touch the swab tips with your fingers.
6. Cap tightly. Label the tube with a Sharpie or pre-prepared label that contains at a minimum the following information: the date, your initials, sample ID, and sample type (*i.e.*, water feature).
7. Place labeled tubes in a ziploc bag and refrigerate swabs until processing.

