
In this study, we are unable to exclude NTM acquisition from direct patient-to-patient contact or via a common environmental source outside the healthcare setting. Evaluation of non-healthcare settings is beyond the scope of this project, but serves as a potential future area of investigation. There may also be a baseline frequency of patient overlap that is not related to transmission events in the healthcare setting that we expect to capture with evaluation of control pairs of subjects. Despite this small sample size, this preliminary data provides insight into the frequency and nature of patient overlap in the healthcare setting and reveals that among CF patients receiving healthcare in the same location, there are opportunities for close direct or indirect contact. In the setting of strict IP&C measures with single patient rooms, healthcare staff gowning and gloving, patients wearing masks, aggressive cleaning procedures between patients, and maintenance of patient-to-patient separation of 6 feet or more, direct and indirect patient overlap should be minimized. However, incidental or unanticipated contacts remain a risk. If patients in fact have no direct or indirect contact, *investigation of the healthcare environment is essential to eliminate a common healthcare-associated environmental source as the point of CF patient NTM acquisition*.

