3 STUDY OBJECTIVES

3.1 Primary Objective

PART A / Epidemiologic Investigation:

The primary objective of the epidemiologic investigation is to facilitate implementation of a stepwise process by which individual Centers perform retrospective epidemiologic evaluation of patients identified by the CO-RDP as part of an NTM cluster.

PART B / Water Biofilm Collection:

The primary objective of water biofilm collection is to determine if NTM strains identified in clusters are related to the strains isolated from water biofilm sources in the CF healthcare setting.

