4 STUDY DESIGN

4.1 Study Overview

PART A / Epidemiologic Investigation:

This study will retrospectively review and collect data from patients with CF and culture positive for an NTM isolate falling in a highly-related cluster, identified by the CO-RDP, within a single CF Care Center. Two control subjects will be identified by the CO-RDP for every subject falling within a cluster. Retrospective epidemiologic data collection and input into REDCap is detailed (**Appendix 1 and 2**). Up to 20 Care Centers will be offered enrollment.

PART B / Water Biofilm Collection:

This study will also collect and analyze water biofilms from a variety of water sources in the healthcare setting including sink faucets, showerheads, shower hoses, ice machines, drinking fountains, and decorative water features. Environmental sampling instructions are detailed (**Appendix 3**).

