5 CRITERIA FOR EVALUATION

5.1 Primary Endpoint

PART A / Epidemiologic Investigation:

Identification of a shared healthcare-associated source(s) between patients in a Care Center with identical NTM isolates.

PART B / Water Biofilm Collection:

Identification of clinically-relevant NTM isolates and prevalent environmental genotypes with in healthcare setting water biofilms.

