5.2 Secondary Endpoints

PART A / Epidemiologic Investigation:

The secondary endpoints are:

- Adherence to CF IP&C guidelines.
- Characterization of points of patient overlap.

PART B / Water Biofilm Collection:

The secondary endpoints are:

- Incidence and prevalence of NTM species/subspecies within healthcare water biofilms.
- Determine if biofilm isolates are highly related to isolates recovered from patients.

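### One step in Appendix 3 sends the sampler to a home showerhead, contradicting Part B's restriction to healthcare water

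*Protocol*

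**What the plan says.** Section 4.1 sets the sampling frame for Part B: "This study will also collect and analyze water biofilms from a variety of water sources in the healthcare setting". Showerheads and shower hoses are in its list of sources. Sections 4.1 and 9 both point to Appendix 3 for the sampling instructions.

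The objective and endpoints keep to that frame. The Part B primary objective in Section 3.1 asks whether cluster strains are "related to the strains isolated from water biofilm sources in the CF healthcare setting". The Section 5.1 primary endpoint is "Identification of clinically-relevant NTM isolates and prevalent environmental genotypes with in healthcare setting water biofilms". A Section 5.2 secondary endpoint is "Incidence and prevalence of NTM species/subspecies within healthcare water biofilms". The discussion of preliminary work in Section 1.2 adds: "Evaluation of non-healthcare settings is beyond the scope of this project".

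The Appendix 3 subsection on non-removable showerheads begins with "Locate the showerhead in your home that is most often used".

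Appendix 3 also contains a dust procedure, which tells the sampler to "sample similar sites in all rooms of NJH and SJH".

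**The concern.** The instruction on where to swab names a place outside the study. Part B exists to judge whether water in the care setting is a plausible source of the clustered strains, so where each swab was taken is part of the measurement. The protocol itself lists home water supplies among suspected NTM sources (Section 1) and cites work finding clinically relevant NTM in showerheads on municipal water (Section 2). A home swab could therefore well be positive.

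If such a swab were handled as a Center sample, two results would be affected. It would count in the prevalence of NTM in healthcare biofilms. It would also enter the comparison of biofilm with patient isolates, where a strain from a shared municipal supply could be read as evidence of a source inside the Center.

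**Working it through.** The protocol states no figure to reproduce, so the check is mainly one of consistency.

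**Where Part B sampling may take place**

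| Place in protocol | Setting |
|---|---|
| Synopsis, Part B design | Healthcare water supplies |
| Section 3.1, primary objective | CF healthcare setting |
| Section 4.1, overview | Healthcare setting |
| Section 5.1, primary endpoint | Healthcare water biofilms |
| Section 5.2, secondary endpoint | Healthcare water biofilms |
| Section 1.2, scope | Non-healthcare settings excluded |
| Appendix 3, non-removable showerhead | The sampler's home |

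The last row conflicts with every other row. No section provides for household samples as a comparator or an additional data set, so the sentence cannot be read as a planned extension.

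**How far the wording reaches.** The home is named only in the sentence that introduces the non-removable showerhead procedure. Numbered step 1 below it simply says to find the non-removable showerhead. The procedures for shower hoses, removable showerhead faces, ice machines, drinking fountains and water features name no home.

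**Whether a home sample could be recognised.** The minimum tube label for this step is date, initials, sample ID and a sample type that denotes the outside of a showerhead. It does not require a facility or room, so the label alone would not separate a home from a hospital showerhead. However, Appendix 3 opens by requiring a GPS record for each sampling site, and this step also requires a photograph. With the sample ID, these allow the location to be traced afterwards. The protocol states no check of them and no exclusion that depends on them.

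**Direction and bound of the effect on prevalence.** Let w be the share of analysed samples that came from homes, p_D the positivity of home samples and p_H that of healthcare samples. If home samples are not removed:

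- pooled prevalence = (1 − w) × p_H + w × p_D
- bias = pooled prevalence − p_H = w × (p_D − p_H)

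Since both positivities lie between 0 and 1, the absolute bias cannot exceed w, and its sign depends on which positivity is larger. The protocol gives none of w, p_D or p_H, so no number can be put in. If nobody follows the sentence literally, w = 0 and the bias is 0.

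**Effect on relatedness.** This comparison looks for matches between biofilm and patient isolates, so even one unrecognised home sample that matched could be reported as a link to the Center. How likely that is cannot be derived from the protocol.

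**The case against.** The strongest reply is that this is stray wording. Everything else in the protocol says healthcare setting. Appendix 3 reads like a generic template, with kitchen and outdoor faucets in one procedure and a tub in another, and many samplers would take the sentence to mean the facility's showerhead. GPS, photograph and sample ID would expose a home sample. The protocol does not even say who collects the samples. An SAP, which was not at hand, might exclude off-site samples.

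Most of this stands, and it limits the point. It does not make the sentence right: an analysis plan might remove a misplaced swab, but it would not correct the instruction that misplaced it.

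A reader might infer more than the text supports:

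- **That the study chose to sample homes.** No objective, endpoint or design statement does so. This is an internal inconsistency.
- **That household samples would pass unnoticed.** The location records argue against that. What is missing is a stated rule for using them.
- **That showerheads as a whole, or several source types, are affected.** Only the non-removable showerhead subsection names a home.
- **That the dust step carries the same risk.** Dust tubes are labelled as dust, so they would not be mistaken for a water outlet, and the step concerns rooms at named institutions, not homes.

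**Conclusion.** The sentence is wrong as written. It contradicts the Part B frame, objective, endpoints and scope statement, in the appendix that Sections 4.1 and 9 cite for sampling. If it is followed literally, out-of-scope biofilm is collected, and it could be counted in healthcare prevalence and in the patient-to-biofilm comparison.

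The size is unknown. It depends on how many samplers take the sentence at its word and on whether anyone reviews the location records. Harm requires both that a home is swabbed and that the sample is then analysed as a Center sample. The point is minor and worth correcting because the correction is so small.

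Separately and lesser still, dust is not a water biofilm and no Part B objective or endpoint uses it, so the dust step has no stated place in the analysis.

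**What to change.** 1. In Appendix 3, replace the opening sentence of the non-removable showerhead procedure with, for example: select a non-removable showerhead in the participating Center's healthcare setting (clinic, hospital or research area). This uses the definition of the healthcare setting already given in Section 2.
2. Add one sentence stating that any sample whose recorded location is outside that setting is excluded from Part B analyses. The GPS record and photograph already required are enough to apply it.
3. Mark the dust step as outside the Part B analysis.

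The replacement should not limit this outlet to rooms used by clustered patients during the chart-extraction window. That window is a pair-specific device of Part A, and applying it here would give one outlet type a different sampling frame from all the others.

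The cost is about three sentences in the protocol. No new data collection is needed. If sampling has already begun, the recorded locations of samples taken under this step should be checked once.
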